1.2 BACKGROUND ON RO7234292

Neuropathological abnormalities in HD appear to be the consequence of a toxic gain-of-function of the mHTT protein (Wexler et al. 1987; Walker 2007; Moumné et al. 2013). Therefore, a therapy that reduces synthesis of the toxic mHTT protein should directly target the primary disease mechanism. As the genetic origin of HD is localized to just one gene, inhibiting the expression of this *HTT* gene is a promising therapeutic option (Stanek et al. 2013).

RO7234292 (RG6042) was originally developed by Ionis Pharmaceuticals, Inc. and was formerly known as ISIS 443139 and IONIS-HTT_{Rx}. This antisense oligonucleotide (ASO) is being developed to reduce the synthesis of all forms of the HTT protein by targeting the *HTT* mRNA from both the wild-type and the mutant alleles and directing its catalytic degradation through the action of ribonuclease H1, an endogenous enzyme present in most mammalian cells (Cerritelli and Crouch 2009; Crooke and Bennett 1996), including cells of interest in the CNS (e.g., neurons and neuroglia). Reduction of the *HTT* gene mRNA could potentially inhibit downstream toxic effects of mHTT and lead to a sustained reversal in HD symptoms.

Pharmacology data support selective targeting of *HTT* mRNA transcripts from both alleles as a potentially safe and effective mechanism for the treatment of HD. Using ASOs targeting human *HTT* mRNA in rodents, significant reduction of mutant *HTT* mRNA transcripts, wild-type HTT mRNA transcripts, and mHTT protein has been achieved throughout most brain regions (Kordasiewicz et al. 2012). Furthermore, transient delivery of these ASOs in transgenic mouse models of HD delayed disease progression and mediated a sustained reversal of disease phenotype that persisted longer than *HTT* mRNA knockdown (Kordasiewicz et al. 2012; Stanek et al. 2013).

Nonclinical proof-of-concept studies with ASOs targeting *HTT* have been conducted in three models of HD, including YAC128 mice expressing the full-length mutant human *HTT* transgene with a 128 CAG repeat expansion, BACHD mice expressing the full-length mutant human HTT genomic sequence with 97 CAG/CAA repeats, and R6/2 mice expressing exon 1 of the mutant human *HTT* gene with 110–135 CAG repeats. These studies demonstrate that ASOs targeting human *HTT* mRNA improve motor function and protect against human HTT transgene expression in YAC128 mice; improve motor function, hypoactivity, and stress response in BACHD mice; and preserve striatal volume and increase survival in R6/2 mice.

The pharmacokinetics (PK) and toxicity of intrathecal (IT) administration of RO7234292, an ASO that targets human *HTT* mRNA, were assessed in cynomolgus monkeys for 13 weeks (biweekly for the first month, then monthly thereafter) at dose levels up to 50 mg/dose (5 bolus administrations, for a total dose of 250 mg) and chronically for 9 months, up to 35 mg/dose (10 bolus monthly administrations for a total dose of 350 mg). The drug was safe and well-tolerated in these studies.

In a first-in-human, Phase I/IIa double-blind, placebo-controlled, dose-escalation study (Clinicaltrials.gov Identifier NCT02519036) (ISIS 443139-CS1) 4 doses of RO7234292 (ranging from 10 mg to 120 mg) were well-tolerated and achieved significant dose-dependent lowering of cerebrospinal fluid (CSF) mHTT protein when administered IT every 4 weeks (Q4W; monthly) to 46 patients with early manifest HD. Exploratory analyses identified a relationship between lowering of mHTT protein and improvement in some clinical measures. Taken together, these data supported further clinical testing to demonstrate definitive clinical benefit of mHTT protein reduction in the CNS. The data from this study also supported the initiation of Study ISIS 443139-CS2 (Study BN40697; Clinicaltrials.gov Identifier NCT03342053), a 15-month, Phase II open-label extension (OLE) study for patients who participated in Study ISIS 443139-CS1.

Preliminary data from analysis conducted when all individuals in Study BN40697 had reached 9 months of treatment showed that a 120 mg every-8-week (Q8W; every 2 months) dosing regimen of RO7234292 achieved a 47% median CSF mHTT lowering at trough (i.e., sample taken immediately before the next dose) and the 120 mg Q4W dosing regimen achieved a 66% median lowering at trough. Both results exceed the 20%–40% target for CSF mHTT lowering at trough and steady state based upon efficacy data from nonclinical models, and exceed the result of approximately 40% median lowering observed in the completed Phase I/IIa study. Details on the most recent information from nonclinical and clinical studies can be found in the RO7234292 Investigator's Brochure.

1.3 STUDY RATIONALE AND BENEFIT-RISK ASSESSMENT

This study is designed to assess the long-term safety and tolerability of IT administered RO7234292 in patients who have completed or have participated in other F. Hoffmann-La Roche, Ltd.–sponsored (hereafter referred to as Roche) and/or Genentech-sponsored studies in HD in the development program for RO7234292. Presently, there are no therapies available to stop or slow the clinical progression of HD, which is relentless until patients experience premature death. The ASO RO7234292 is designed to target the cause of HD and offers the potential to meet this unmet medical need.

To date, nonclinical and clinical data support further investigation of RO7234292 in patients with HD. Current planned or ongoing studies in the RO7234292 clinical development plan are designed for durations of up to approximately 2 years. This study is designed to collect safety data in a larger number of patients and will also study the

benefit and potential risks of RO7234292 when administered by IT bolus injection Q8W or every 16 weeks (Q16W) over a longer period.

Review of preliminary 9-month safety and tolerability data for RO7234292 from the Phase II OLE (Study BN40697) suggested that, relative to the Q4W treatment regimen, the Q8W treatment regimen may be more suitable for chronic IT dosing, as evidenced by improved adherence to the less frequent regimen. This is supported by observations of fewer overall AEs, decreased proportion of patients with moderate AEs, and fewer AEs considered possibly related to study drug in the Q8W regimen compared to the Q4W regimen (for details see the RO7234292 Investigator's Brochure).

There were no acute safety concerns meriting a change to the ongoing Phase II OLE study protocol (Study BN40697). However, given the 9-month CSF mHTT results, which suggested a longer than anticipated duration of effect of RO7234292 on CSF mHTT lowering, it is not necessary to use a Q4W paradigm to test the dose rationale. As a result, the results from OLE Study BN40697 justified a change in Study BN40955 to explore less frequent dosing regimens by continuing the Q8W RO7234292 arm and replacing the Q4W arm with a Q16W arm.

The existing dose rationale tests a more frequent dosing regimen (i.e., 120 mg Q8W), which from present data is anticipated to maintain trough CSF mHTT reduction of at least approximately 40%, and a less frequent regimen (i.e., 120 mg Q16W), which is still anticipated to lower mHTT acutely, but will allow greater recovery of HTT levels between doses. From present data, trough CSF mHTT reduction of approximately 25% is predicted to be maintained in a 120 mg Q16W paradigm.

A pre-planned review of safety and efficacy data from the GENERATION HD1 phase III Study BN40423, as well as available open-label data, was conducted by the BN40423 independent Data Monitoring Committee (iDMC). Following review of the data, the iDMC recommended that all dosing (120 mg Q8W and Q16W and placebo) in Study BN40423 be permanently stopped. This iDMC recommendation was not based on any new emergent safety concerns, but on a totality of evidence indicating that the treatment arms demonstrated unfavorable safety and efficacy trends compared to the placebo arm over time. The iDMC also made a recommendation for the ongoing patients in the Study BN40423 to be followed for safety and efficacy outcomes until study completion as per protocol, without study drug administration. Study BN40955 (open-label extension [OLE]) is exploring the same dosing regimens (i.e., tominersen [RO7234292] 120 mg Q8W and Q16W); therefore, the Sponsor made a decision to pause dosing in the OLE until further data assessments can be conducted.

The known potential risks associated with RO7234292 and additional risks related to lumbar punctures (LPs), along with mitigation measures, are elaborated in Section 5.1.

2. OBJECTIVES AND ENDPOINTS

This study will evaluate the long-term safety and tolerability of RO7234292 in patients with HD. In addition, the study will obtain long-term data on the efficacy, immunogenicity, exposure, and biomarkers of RO7234292. Specific objectives and corresponding endpoints for the study are outlined below.

Objectives will be achieved primarily by using data collected in this OLE study, but may also be informed by using previously collected data from participants of the preceding Roche studies. Data may be linked and, if appropriate, may be analyzed by pooling data.

2.1 SAFETY OBJECTIVE

The safety objective for this study is to evaluate the safety and tolerability of RO7234292 on the basis of the following endpoints:

- Incidence and severity of AEs, with severity determined according to the Adverse Event Severity Grading Scale (see [Table 3](#))
- Change from baseline in targeted vital signs
- Change from baseline in physical findings
- Change from baseline in neurological findings
- Change from baseline in behavioral findings, as assessed by the Columbia-Suicide Severity Rating Scale (C-SSRS)
- Change from baseline in cognition
- Change from baseline in targeted ECG results
- Change from baseline in targeted clinical laboratory test results
- Relationship between laboratory parameter change and safety-targeted endpoints
- Relationship between magnetic resonance imaging (MRI) parameter change and safety-targeted endpoints

2.2 EXPLORATORY EFFICACY OBJECTIVES

The exploratory efficacy objective for this study is to evaluate the efficacy of RO7234292 on the basis of the following endpoints:

- Change from baseline in the composite Unified Huntington's Disease Rating Scale (cUHDRS) score as assessed Q16W
- Change from baseline in scores for the following individual scales as assessed Q16W:
 - Total Functional Capacity Scale.
 - Total Motor Score (TMS).
 - Symbol Digit Modalities Test (SDMT).
 - Stroop Word Reading (SWR) test.

- Change from baseline in the Clinical Global Impression, Severity Scale (CGI-S) score as assessed Q16W
- Proportion of patients with an unchanged or improved score on the Clinical Global Impression, Change Scale (CGI-C) score from baseline as assessed Q16W
- Change from baseline in the Huntington's Disease Daily Activities Scale (HD-DAS) score as assessed Q16W
- Change from baseline in the sensor-based measures collected by the Roche HD mobile application (app; smartphone and wrist-worn wearable) as assessed Q16W

2.3 EXPLORATORY PHARMACOKINETIC/PHARMACODYNAMIC OBJECTIVES

The exploratory PK objective for this study is to characterize the RO7234292 PK trough plasma and trough CSF samples on the basis of the following endpoints:

- Trough concentration of RO7234292 in plasma at specified timepoints
- Trough concentration of RO7234292 in CSF at specified timepoints

The exploratory PK/pharmacodynamic (PK/PD) objective for this study is to evaluate potential relationships between drug exposure and the efficacy and safety of RO7234292 on the basis of the following endpoints:

- Relationship between trough plasma and/or trough CSF concentrations of PK parameters for RO7234292 and efficacy endpoints
- Relationship between trough plasma and/or trough CSF concentrations of PK parameters for RO7234292 and safety endpoints

2.4 EXPLORATORY IMMUNOGENICITY OBJECTIVES

The exploratory immunogenicity objectives for this study are as follows:

- To evaluate the immune response to RO7234292 on the basis of the following endpoints:
 - Incidence of anti-drug antibodies (ADAs) at specified timepoints relative to the prevalence of ADAs at baseline.
 - Determination of the ADA specificity followed by assessments of the magnitude (titer) of the ADA response.
- To evaluate potential effects of ADAs on the basis of the following endpoint:
 - Relationship between ADA status and efficacy, safety, or PK endpoints.

2.5 EXPLORATORY BIOMARKER OBJECTIVE

The exploratory biomarker objective for this study is to identify biomarkers that are early surrogates of efficacy, are associated with progression to a more severe disease state (i.e., prognostic biomarkers), are associated with acquired resistance to RO7234292, are associated with susceptibility to developing AEs or can lead to improved AE monitoring or investigation (i.e., safety biomarkers), can provide evidence of RO7234292 activity

(i.e., PD biomarkers), or can increase the knowledge and understanding of disease biology and drug safety, on the basis of the following endpoints:

- Relationship between biomarkers (e.g., tau and neurofilament light chain protein [NfL]) in plasma and CSF (listed in Section 4.5.6) and efficacy, safety, PK, immunogenicity, or other biomarker endpoints
- Relationship between imaging biomarkers and efficacy, safety, PK, immunogenicity, or other biomarker endpoints

2.6 HEALTH STATUS UTILITY OBJECTIVE

The exploratory health status utility objective for this study is to evaluate health status utility scores of patients treated with RO7234292 on the basis of the following endpoint:

- Change from baseline in patient-reported EuroQol 5-Dimension, 5-Level Questionnaire (EQ-5D-5L) Index and Visual Analog Scale (VAS) scores at specified timepoints

3. STUDY DESIGN

3.1 DESCRIPTION OF THE STUDY

3.1.1 Overview of Study Design

This OLE study will evaluate the long-term safety and tolerability of RO7234292 administered IT to patients with HD. In addition, the study will obtain long-term data on the efficacy, immunogenicity, exposure, and biomarkers of RO7234292.

Effective 22 March 2021, dosing is paused, including enrollment. Patients already on the study will continue to be followed for safety and efficacy outcomes until study completion (see [Appendix 1a](#), [Appendix 1b](#), and [Appendix 2b](#)).

Only patients with prior enrollment in a Roche-sponsored or Genentech-sponsored study in HD for the RO7234292 development program that made provision for entry into an OLE study will be eligible for this OLE study. The preceding Roche-sponsored or Genentech-sponsored study must have been approved by the relevant national competent authority and applicable Institutional Review Board (IRB)/Ethics Committee (EC) in a country in order for a patient from that country to be included in the OLE.

For patients who have participated in previous Roche studies, entry into this long-term, open-label extension study will occur at an inclusion visit. This inclusion visit is a combined visit with the preceding study's last applicable visit where patients are due for their end of treatment visit, last CSF collection, or safety follow-up unless otherwise specified, and serves as the baseline visit for the long-term, open-label extension study. For participants who have not participated in a previous Roche study, a separate screening visit will occur to determine eligibility into the long-term, open-label extension study. Patients who successfully meet eligibility criteria will then enter the study and attend the baseline study visit. Patients who were enrolled in Study BN40423 before implementation of Version 4 of that protocol will be prematurely discontinued by the

Sponsor from Study BN40423 and offered treatment in this study (Study BN40955) when it is available at sites.

If dosing at the inclusion visit is not possible, the Medical Monitor should be consulted and a short treatment interruption may be permitted. For patients entering from Study BN40423 prior to implementation of Protocol Version 4, the inclusion visit should occur at the end-of-treatment visit for Study BN40423.

Patients who were screened and eligible for the placebo-controlled Phase III Study BN40423 (Generation-HD1) but were not randomized prior to the close of Study BN40423 enrollment due to logistical challenges resulting from the COVID-19 pandemic, will be offered open-label RO7234292 as part of this study, Study BN40955. Participation can occur once approved and available at sites and so long as the patient meets Study BN40955 eligibility. These patients will undergo screening assessments during a 4-week screening period. A maximum of 1 re-screening will be allowed within 8 weeks of an initial screening failure in Study BN40955.

The CAG repeat length testing from Q2 Solutions will be accepted for this study. If re-screening is required, the CAG repeat length testing from Q2 Solutions does not need to be repeated. The screening MRI and viral serology from the initial screening, including from other Roche RO7234292 studies, may be acceptable as part of the screening assessments if performed within 12 weeks of the inclusion visit.

For patients entering from Study BN40697, in the event of any delay in start-up activities where it is not possible to conduct the inclusion visit at the time of the last applicable visit in Study BN40697, a separate inclusion visit should be scheduled (see [Appendix 1a](#)).

Upon completion of the inclusion visit, eligible patients will receive either 120 mg RO7234292 Q8W (RO7234292 Q8W arm) or 120 mg RO7234292 Q16W (RO7234292 Q16W arm) by bolus IT injection. Patients will be assigned to treatment groups as described below and in [Table 1](#):

- Patients who previously received open-label 120 mg RO7234292 Q4W in a preceding study or who are currently receiving open-label 120 mg RO7234292 Q4W in Study BN40955 will be randomly allocated to receive 120 mg of RO7234292 Q8W or 120 mg of RO7234292 Q16W.

Patients who previously received open-label 120 mg of RO7234292 Q8W in a preceding study or are currently receiving open-label 120 mg RO7234292 Q8W in Study BN40955 will receive 120 mg of RO7234292 Q8W.

Patients who previously received placebo in a preceding study will be randomly allocated to receive either 120 mg of RO7234292 Q8W or RO7234292 Q16W.

The drug administered at the inclusion visit will be the last dose or at the last CSF collection of the preceding study (if the inclusion visit is at the last visit in

the preceding study) or will be the first dose in Study BN40955 if a separate inclusion visit is required (see [Appendix 1a](#)).

- After implementation of Study BN40955 Protocol Version 3, patients who are already enrolled in Study BN40955 will sign the amended Informed Consent Form (ICF) at or before their next clinic visit, and will be assigned to either the 120 mg RO7234292 Q8W or 120 mg RO7234292 Q16W arm, and then follow the schedule of activities for Protocol Version 3 (see [Appendix 1a](#))—matching treatment week according to [Appendix 2](#)—at the clinic visit and going forward.
- Patients who did not previously receive treatment with RO7234292 (e.g., from a natural history study, eligible patients from Study BN40423 study who were not randomized due to logistical challenges resulting from the COVID-19 pandemic) or received short-term treatment (≤ 4 doses) with a treatment-free follow-up period will be randomly allocated to receive 120 mg of RO7234292 Q8W or 120 mg of RO7234292 Q16W. The first dose in Study BN40955 will take place at the inclusion visit.
- Patients who previously received blinded placebo Q8W will be randomly allocated to receive 120 mg of RO7234292 Q8W or 120 mg of RO7234292 Q16W. The first dose in Study BN40955 will take place at the inclusion visit.
- Patients who previously received blinded 120 mg of RO7234292 Q8W will receive open-label 120 mg of RO7234292 Q8W.
- Patients who previously received blinded 120 mg of RO7234292 Q16W will receive open-label 120 mg of RO7234292 Q16W.

For patients who enrolled from Study ML41885, the inclusion visit will take place at the first safety follow-up visit of Study ML41885 (i.e., safety follow-up [SFU1]). The drug administered at the inclusion visit will be the first dose in Study BN40955. Patients who consent to be enrolled into this study (Study BN40955) will be assigned to a treatment group as shown below:

- Patients who received open-label 120 mg of RO7234292 Q16W will receive open-label 120 mg of RO7234292 Q16W.

Patients enrolled in Study BN40423 prior to implementation of Protocol Version 4 will be prematurely discontinued from that study. Patients who consent to be enrolled into this study (Study BN40955) will be assigned to treatment groups as shown below:

- Patients who received blinded 120 mg of RO7234292 Q4W will be randomly allocated to receive open-label 120 mg of RO7234292 Q8W or 120 mg of RO7234292 Q16W.
- Patients who received blinded 120 mg of RO7234292 Q8W will receive open-label 120 mg of RO7234292 Q8W.
- Patients who received blinded placebo Q4W will be randomly allocated to receive open-label 120 mg of RO7234292 Q8W or 120 mg of RO7234292 Q16W.

Table 1 Treatment Regimen in Study BN40955 Based on Previous Study Treatment

Preceding Study Treatment	Treatment Regimen
Open-label 120 mg RO7234292 Q4W	Randomized 1:1 to 120 mg RO7234292 Q8W or 120 mg RO7234292 Q16W
Open-label 120 mg RO7234292 Q8W	120 mg RO7234292 Q8W
No treatment or ≤ 4 doses of 120 mg or less RO7234292 with a treatment-free follow-up period	Randomized 1:1 to 120 mg RO7234292 Q8W or 120 mg RO7234292 Q16W
Blinded placebo Q8W	Randomized 1:1 to 120 mg RO7234292 Q8W or 120 mg RO7234292 Q16W
Blinded 120 mg RO7234292 Q8W	120 mg RO7234292 Q8W
Blinded 120 mg RO7234292 Q16W	120 mg RO7234292 Q16W

Table 1 Treatment Regimen in Study BN40955 Based on Previous Study Treatment (cont.)

Preceding Study Treatment	Treatment Regimen
For Patients enrolled into Study BN40423 prior to implementation of Study BN40423 Protocol Version 4:	
Blinded 120 mg RO7234292 Q4W	Randomized 1:1 to 120 mg RO7234292 Q8W or 120 mg RO7234292 Q16W
Blinded 120 mg RO7234292 Q8W	120 mg RO7234292 Q8W
Blinded Placebo Q4W	Randomized 1:1 to 120 mg RO7234292 Q8W or 120 mg RO7234292 Q16W
Open-label 120 mg RO7234292 Q16W	120 mg RO7234292 Q16W

Q4W=every 4 weeks; Q8W=every 8 weeks; Q16W=every 16 weeks.

For patients who did not previously receive treatment with RO7234292 (e.g., from a natural history study) or received short-term treatment (≤ 4 doses), the end of study visit for the preceding study will serve as the inclusion visit for Study BN40955. For patients who completed the full treatment course in the preceding study, the inclusion visit for Study BN40955 will take place at the visit at which the last dose was administered. For patients enrolled in Study BN40423 prior to implementation of Protocol Version 4 who were prematurely discontinued, the inclusion visit for Study BN40955 will take place at the end-of-treatment visit for Study BN40423. For patients entering from Study BN40697, in the event of any delay in start-up activities where it is not possible to conduct the inclusion visit for Study BN40955 at the time of last applicable visit in Study BN40697, a separate inclusion visit should be scheduled (see [Appendix 1a](#)). At the inclusion visit for Study BN40955, clinical ratings and assessments that are common between the preceding study and Study BN40955 will be completed once and will serve both studies. Clinical ratings and assessments required in Study BN40955 that were not completed as part of the preceding study will also need to be completed at the inclusion visit. Patients who were eligible for Study BN40423 (GENERATION-HD1) but were not randomized due to logistical challenges resulting from the COVID-19 pandemic will undergo screening and inclusion visits, see details of assessments in [Appendix 1b](#) and [Appendix 5](#).

Patients will undergo safety and tolerability evaluations that include neurologic examinations, vital signs, ECGs, clinical laboratory tests, Montreal Cognitive Assessment (MoCA), C-SSRS, neuroimaging assessments and reporting of AEs and concomitant medications, as detailed in [Appendix 1a](#) and [Appendix 1b](#). Patients enrolling from Study BN40697 will have an optional MRI of brain and spine with contrast media, in addition to the other brain neuroimaging assessments.

In case of a failed IT bolus dosing procedure (e.g., due to an inadequate establishment of access to the IT space), a second dosing attempt may occur up to 7 days after the originally scheduled dosing attempt. For this additional visit, safety and tolerability evaluations on the day of LP administration will be performed as detailed in [Appendix 1a](#) and [Appendix 1b](#), including neurological examination (predose and postdose), vital signs, and a review of AEs and concomitant medication. If the second dosing attempt occurs more than 72 hours after the last coagulation panel and platelets test, local laboratory analysis of coagulation factors (INR and/or PT, aPTT) and platelets need to be conducted again and results reviewed prior to the LP attempt (see [Appendix 1a](#) and [Appendix 1b](#)).

Telephone safety follow-up calls will be conducted between dosing visits to check for any change in patient status (i.e., AEs, concomitant medications) since last visit (see [Appendix 2](#)). Depending on the patient's health status, an unscheduled clinic visit may be arranged. If a patient is due for a telephone safety call and they are in-clinic then this telephone safety follow-up call can be completed in-clinic at the site's discretion. As a result of the COVID-19 pandemic, only where sites are impacted, these telephone safety calls can be conducted instead of an in-clinic visit.

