3.3.2 Rationale for Biomarker Assessments

3.3.2.1 Cerebrospinal Fluid Biomarkers

Measurement of protein levels in the CSF offers the potential to monitor molecular changes that take place in the CNS. A toxic gain-of-function mechanism of mHTT protein is widely considered to be the primary driver of disease pathophysiology in HD (Wild and Tabrizi 2017). Mutant HTT protein in human CSF is associated with disease stage and severity and with biomarkers of neuronal damage, including CSF (NfL) and CSF tau levels (Wild et al. 2015). Neurofilament light chain protein levels in CSF predict progressive MRI measures of brain atrophy, as well as progressive clinical decline in patients (Wild and Tabrizi 2017). Longitudinal analysis of mHTT, NfL, tau and other biomarkers related to HD, neurodegeneration, and inflammation in CSF may extend the current understanding of HD pathophysiology and progression and provide further data on how these putatively prognostic and potentially predictive biomarkers will respond to disease-modifying treatment.

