Appendix 1a

Schedule of Activities for All Patients Except Those Undergoing Screening (cont.)

CGI-C=Clinical Global Impression, Change; CGI-S=Clinical Global Impression, Severity; C-SSRS=Columbia-Suicide Severity Rating Scale; CSF=cerebrospinal fluid; cUHDRS=composite Unified Huntington's Disease Rating Scale; eCRF=electronic Case Report Form; EoT=end-of-treatment; EQ-5D-5L=EuroQol 5-Dimension, 5 Level Questionnaire; HD=Huntington's disease; HD-DAS=HD Daily Activities Scale; LP=lumbar puncture; MoCA=Montreal Cognitive Assessment; MRI=magnetic resonance imaging; NODDI=Neurite Orientation Dispersion and Density Imaging; PK=pharmacokinetic; SDMT=Symbol Digit Modalities Test; SFU=safety follow-up; SWR=Stroop Word Reading; TFC=Total Functional Capacity Scale; TMS=Total Motor Score; Q8W=every 8; Q16W=every 16 weeks; Q32W=every 32 weeks.

Notes: All assessments should be performed at the scheduled visit, unless otherwise specified. On treatment days, all assessments should be performed prior to dosing, unless otherwise specified.

- ^a Inclusion visit should be the last applicable visit of the preceding study as defined in Section 3.1.1. For patients entering from Study BN40423 prior to implementation of Protocol Version 4, the inclusion visit should occur at the end-of-treatment visit for Study BN40423. For patients entering from Study BN40697, in the event of any delay in start-up activities where it is not possible to conduct the inclusion visit at the time of the last applicable visit in Study BN40697, a separate inclusion visit should be scheduled 4 weeks or 8 weeks (± 1 week) for a patient previously treated Q4W or 8 weeks (± 1 week) later for a patient previously treated Q8W.
- ^b If dosing at the inclusion visit is not possible, the Medical Monitor should be consulted and a short treatment interruption may be permitted.
- ^c Patients who complete treatment (e.g., will continue treatment on commercially available drug) or who discontinue study drug prematurely will return to the clinic for a treatment completion visit 4 weeks (± 7 days) after the decision to discontinue. For patients continuing treatment with RO7234292 outside of the study, the end of study visit should occur before the patient's next dose of RO7234292.
- ^d Safety follow-up visit occurs +20 weeks after EoT.
- ^e Excluding MRIs, which have a visit window of -14 to -7 days.

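### The single OLE baseline is on-drug for some patients and drug-free for others in the same arm, which mainly blurs change in drug-responsive CSF biomarkers and undercounts induced ADA

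*Combined protocol and SAP*

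**What the plan says.** Section 3.1.1 combines the inclusion visit with the last applicable visit of the preceding study and states that it "serves as the baseline visit for the long-term, open-label extension study". For patients who completed a full treatment course, the inclusion visit "will take place at the visit at which the last dose was administered". The notes to Appendix 1a add: "On treatment days, all assessments should be performed prior to dosing, unless otherwise specified".

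Entry differs for other groups:
- Untreated and short-course patients (up to 4 doses, then a treatment-free period) enter at the end-of-study visit of the preceding study.
- ML41885 patients enter at their first safety follow-up visit.
- BN40423 patients enrolled before Version 4 of that protocol enter at their end-of-treatment visit.
- If start-up is delayed for BN40697 patients, "a separate inclusion visit should be scheduled 4 weeks or 8 weeks" later for those previously on Q4W, and 8 weeks later for those on Q8W.

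Table 1 gives naive, short-course, ex-placebo and prior Q4W patients the same assignment: "Randomized 1:1 to 120 mg RO7234292 Q8W or 120 mg RO7234292 Q16W". Others are not randomized; for example, "Patients who previously received blinded 120 mg of RO7234292 Q8W will receive open-label 120 mg of RO7234292 Q8W". Patients on Q4W inside this study are also reassigned: those "who are currently receiving open-label 120 mg RO7234292 Q4W in Study BN40955 will be randomly allocated" to Q8W or Q16W.

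Section 6.5 summarises by treatment, and Sections 6.6 and 6.9 by arm, at each assessment time. All three give absolute values and change from baseline, and none mentions prior exposure. Section 6.8 defines ADA incidence relative to the baseline sample.

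**The concern.** Each arm contains patients whose baseline already carries a drug effect and patients whose baseline does not. For a measure the drug moves quickly, such as CSF mHTT, change from baseline then depends on what the patient received before entry as well as on the current regimen. A by-arm mean change would partly describe the rollover mix.

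The ADA rule has the same weakness in a sharper form. Incidence is an objective in Section 2.4, and antibodies induced by RO7234292 before entry are not counted in it.

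The pause adds a further reading problem, because CSF for biomarkers is still taken every 16 weeks. If levels recover, a patient who entered on drug will appear to rise above baseline, while a patient who entered drug-free returns to it.

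**Working it through.** The plan states no figure for this point, so there is none to reproduce. The check has three parts.

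**1. CSF mHTT, illustrative.** Inputs, from Sections 1.2 and 3.3.1: median trough lowering of 66% on Q4W and 47% on Q8W after nine months in BN40697; predicted median trough lowering of 20% to 25% on Q16W; about 40% lowering after 3 or 4 doses of 120 mg. Medians and predictions are treated as constants, with the pre-drug level set to 100. The residual levels are:
- Q4W: 100 - 66 = 34
- Q8W: 100 - 47 = 53
- Q16W: 75 to 80
- after 3 or 4 doses: 60

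Reading against the OLE baseline = (level on OLE regimen / level at OLE baseline) - 1.

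| Status at OLE baseline | Level at baseline | Reading on Q8W (level 53) | Reading on Q16W (level 75 to 80) |
|---|---|---|---|
| Naive or ex-placebo | 100 | 53/100 - 1 = -47% | -25% to -20% |
| Continuing same regimen | 53, or 75 to 80 | 53/53 - 1 = 0% | 0% |
| Prior Q4W at nine-month median | 34 | 53/34 - 1 = +56% | +121% to +135% |
| Prior Q4W at 40% lowering | 60 | 53/60 - 1 = -12% | +25% to +33% |

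Within a column, all patients are at the same mHTT level.

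The by-arm mean follows the mix. If a share s of the Q8W arm are Q8W continuers and the rest are naive, the mean reading is (1 - s) x (-47%). For s = 0, 0.25, 0.5, 0.75 and 1 this gives -47%, -35%, -24%, -12% and 0%. These shares are assumed; the documents give none.

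If mHTT recovered fully during the pause (also an assumption), a Q8W entrant would read 100/53 - 1 = +89% and a naive entrant 0%, both at the same level.

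**2. Size of the Q4W group.** Section 5.1.1 gives 16 Q4W patients as 69.6% in BN40697, so 16/0.696 = 23. It gives 14 as 40% in the BN40423 original-design cohort, so 14/0.40 = 35. At most 23 + 35 = 58 patients could enter from these two Q4W pools, divided between the two arms. That is 58/1100 = 5.3% of planned enrollment. The level of 34 is documented only for the BN40697 pool. Patients on Q4W inside BN40955 overlap with or add to this group in unknown number, but their defined baseline is their earlier inclusion visit, so 34 need not apply to them.

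**3. ADA rule.** Take two patients who both became ADA-positive because of RO7234292.
- Patient A is naive at entry, negative at the inclusion visit and positive later. Section 6.8 counts this as treatment-induced incidence.
- Patient B became positive in the preceding study and has titer T at the inclusion visit. B counts in baseline prevalence. If no later titer reaches 4T, Section 6.8 classes B as post-baseline ADA-negative (treatment unaffected).

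Both have drug-induced ADA, but only A enters the incidence.

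**The case against.** The strongest reply is that an extension study normally takes its own entry visit as baseline, and that everything here is descriptive. That stands for clinical scales, MRI and routine laboratory values, where only change before entry is hidden. Absolute values are tabulated too, and adverse event incidence does not use a baseline value.

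It is also fair that change in mHTT is not a listed endpoint. Section 2.5 lists relationships between biomarkers and other endpoints, and the text in Section 3.3.2.1 on "Longitudinal analysis of mHTT, NfL, tau and other biomarkers related to HD, neurodegeneration, and inflammation in CSF" is rationale, not an analysis specification. Section 6.9 nevertheless tabulates biomarker change by arm, so a reader of those tables would meet the problem.

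Section 2 permits linkage and pooling, Section 6.7 permits pooled PK/PD modelling, and Sections 6.6 and 6.9 leave room for later modelling. These are real routes to a better analysis, but all but the core modelling in 6.7 are optional and none defines another baseline. No separate SAP text was supplied, so the point is only that the protocol states no split.

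Delayed BN40697 entrants are not clearly recovered. Delays of 4 weeks after Q4W and 8 weeks after Q8W match the prior dosing interval. For 8 weeks after Q4W dosing, Section 3.3.1 reports at least 35% lowering in all 5 sampled 120-mg Phase I/IIa patients.

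On ADA, baseline prevalence and titers are reported, so carried-over positives stay visible. They cannot be told apart from pre-existing reactivity.

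**Conclusion.** The point holds at the level of a cheap improvement. Applying the stated rules gives by-arm biomarker changes that depend on prior exposure (-47% against 0% at one Q8W level), and ADA induced before entry is undercounted as incidence. The percentages assume steady-state trough values equal to the protocol's medians and predictions.

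A reader might infer three stronger things that the documents do not support:
- **That the arm-level mHTT change is distorted by a known amount, or reverses sign.** The rollover mix is not given, so no arm-level figure can be stated. The uneven cohort sizes implied by Section 5.1.1 for August 2020 (30/0.229 = 131 on Q8W and 11/0.151 = 73 on Q16W) fit the non-random assignments in Table 1, but do not show how many patients entered on drug.
- **That the large positive readings for Q4W switchers are typical.** They rest on one nine-month median and a small subgroup.
- **That the safety or efficacy conclusions are invalid.** No test, power statement or adverse event rate depends on this baseline.

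**What to change.** In Section 6 or the SAP:
- Keep the OLE inclusion-visit baseline. For CSF and plasma biomarkers, CSF safety laboratory values, and ventricular and brain volume MRI, add a second baseline: the last comparable value before the first-ever active RO7234292 dose, from linked preceding-study data where available.
- Present change tables for these measures within arm by exposure status at the OLE baseline: naive or placebo; continuing the same regimen; Q4W before entry; short or interrupted prior course. Show patients switched from Q4W within BN40955 separately, because their baseline is their earlier inclusion visit.
- Leave CGI-C as it is. It is rated as change since starting the study (Section 4.5.10.8) and cannot be re-baselined.
- Summarise off-drug visits during the pause by time since last dose. A split only at 22 March 2021 would mix patients still within a normal dosing interval with patients long off drug.
- In Section 6.8, classify treatment-induced and treatment-enhanced ADA against the pre-first-dose sample where one exists. Otherwise report carried-over positives as a separate category.
- Hold exposure-split tables for rollovers from a still-blinded study until it is unblinded (Section 4.2). Open-label and natural-history entrants and the original-design BN40423 cohort, already unblinded per Section 5.1.1, need not wait.

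The cost is wording, data linkage and a limited set of extra tables, with no new visits or samples. Some patients will lack a comparable pre-drug value and stay on the OLE baseline. These may include BN40697 patients first dosed in the Phase I/IIa study, whose comparability cannot be checked from these documents.
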